2.2.7 Early Trial Discontinuation

If a subject is withdrawn from the trial, the Sponsor will be informed immediately, and the subject will be considered an early-termination subject.

If there is a medical reason for withdrawal, the subject will remain under the supervision of the Investigator at least until the medical situation has resolved.

Regardless of the reason for withdrawal, the subject will be asked to return to the site approximately 4 weeks (+1 week) from the date of early trial discontinuation. After this visit, no further visits will occur.

In cases where further site visits are not possible, subjects should be asked if they would allow the Investigator to continue contacting them and reporting their safety data for 4 weeks after early trial discontinuation.

Reason for withdrawal and the date of discontinuation from the trial should be documented under the following categories:

1. The subject chooses to withdraw

2. The Investigator judges it necessary due to non-compliance with trial procedures (including if the subject loses the ability to give consent)
3. The Investigator judges it necessary to protect the subject's best interest
4. Medical considerations have emerged including difficulties with obtaining or completing required protocol assessments that, in the opinion of the Investigator, potentially affect the safety of the subject. For example, this may include inability to obtain blood samples for safety assessments
5. The subject is pregnant
6. The clinical trial is terminated by the Sponsor
7. The iSRC has recommended it

Subjects who discontinue the trial prematurely will be asked to have ADA samples drawn at 4 (± 2) and 8 (± 2) weeks after an Early Trial Discontinuation visit (refer to Table 2 and Section 5.9.2).

2.2.7.1 Subjects "Lost to Follow-up" Prior to Last Scheduled Visit

A subject is considered lost to follow-up when the Investigator cannot reach the subject. If contact details are available and permission has been obtained, the subject's relatives should be contacted by phone to obtain a reason for the subject not attending a visit (e.g., an AE). If at least three phone calls or other contact efforts (e.g., e-mails, text messages) at different times during a course of 3 weeks are not answered, a registered letter should be sent to the subject. All contact attempts should be documented in the subject's source documents. If the subject decides to withdraw early for the trial, the Investigator should encourage the subject to continue with follow-up safety assessments. If the subject returns to the site at a later time point, the Sponsor should be informed to discuss further steps.

2.2.7.2 Replacement of Subjects

Subjects that discontinue/withdraw after enrollment/randomization will not be replaced.

2.2.8 Screen Failures

The following data will be collected and entered into the electronic Case Report Form (eCRF) for all subjects that are screen failures:

- Date of informed consent form (ICF) and screening visit date
- Underlying disease history, GI-aGVHD history, history of transplant
- Demographics
- Eligibility criteria
- Screen failure reason and date
- Serious AEs, trial procedures-related AEs
- Concomitant medications/procedures related to AEs

If the subject does not meet the eligibility criteria, the subject will be considered a screen failure.

Subjects that failed screening may be rescreened once at a later stage if the reason for screen failure has changed over time (e.g., out of range laboratory values have resolved). Re-screening should occur at least 2 weeks after the time of screen failure and require (i) re-consenting and (ii) Sponsor approval. Subjects who are re-screened will receive a new subject number.

All screening assessments (except colonoscopy/CT colonography/MR enterography) will need to be repeated for the re-screened subject. **In Germany**, only colonoscopies or MR enterographies (not colonographies) can be performed.

2.3 End of Trial Definition

The end of the trial is defined as the last subject's last visit.

The Sponsor may terminate the trial early according to certain circumstances, for example, but not restricted to:

- Ethical concerns
- Insufficient recruitment
- When the safety of the subjects is doubtful or at risk
- Alterations in accepted clinical practice that make the continuation of a clinical trial unwise
- Early evidence of benefit or harm of the experimental intervention

3 TRIAL POPULATION

3.1 Number of Subjects

This trial will include approximately 34 adult and pediatric subjects (12 years or older on the day of screening) who have SR lower GI-aGVHD. **In Germany and France**, only subjects 18 years old and above will be included in this trial.

Sufficient subjects will be screened to allow randomization of approximately 30 subjects to one of two treatment arms (low dose or high dose based on three body weight bands). Up to a further four subjects with a weight of 40.0–<50.0 kg will be treated with apaglutide 2.5 mg (LBW dose).

3.2 Eligibility Criteria

3.2.1 Inclusion Criteria

1. Signed informed consent for this trial prior to any trial specific assessment. A signed assent form will also be required for all subjects under the age of 18 years
2. Male or female subjects aged 12 years or above at the time of consent and who weigh a minimum of 40.0 kg. Only subjects aged 18 years and above will be included **in Germany and France**
3. Have undergone alloSCT from any donor source (matched unrelated donor, sibling, haplo-identical) using bone marrow, peripheral blood stem cells, or cord blood. Recipients of non-myeloablative, myeloablative, and reduced intensity conditioning are eligible
4. Evident myeloid and platelet engraftment confirmed prior to trial medication start:
 - a. Absolute neutrophil count $>1000/\text{mm}^3$
and
 - b. Platelets $\geq20,000/\text{mm}^3$
5. Use of growth factor supplementation (granulocyte-colony stimulating factor and granulocyte-macrophage-colony stimulating factor) and transfusion support is allowed
6. Clinical diagnosis of lower GI-aGVHD, **MAGIC Stage 1–4** prior to randomization. Suitable diagnostic procedures should be implemented to exclude alternative reasons for diarrhea; these include (but not limited to) fecal cultures and lower gut biopsy with histological assessment for infectious diseases
6. Clinically confirmed SR lower GI-aGVHD defined as subjects administered SS, given alone, or combined with CNIs and either:
 - a. Disease progression based on organ assessment after 3 days of systemic MP $\geq2 \text{ mg/kg/day}^3$ ([or prednisone dose $\geq2.5 \text{ mg/kg/day}$] or equivalent) \pm CNIs

³ The SS dose should be calculated based on the subject's actual weight, within the maximum lower margin of 15% from the calculated dose

or

b. Did not improve after 7 days of treatment with systemic MP ≥ 2 mg/kg/day³ ([or prednisone dose ≥ 2.5 mg/kg/day] or equivalent)

or

c. Progressed to a new organ after treatment with systemic MP ≥ 2 mg/kg/day³ ([or prednisone dose ≥ 2.5 mg/kg/day] or equivalent) for skin and upper GI-aGVHD

or

d. Recurred during or after a steroid taper. Initial dose should be ≥ 2 mg/kg/day³ MP (or equivalent) systemic MP ([or prednisone dose ≥ 2.5 mg/kg/day] or equivalent)

7. Treatment with SS plus RUX (RUX started concomitantly to apaglutide or a maximum of 72 hours before apaglutide initiation)

8. Women of childbearing potential must agree to use a highly effective method of contraception and refrain from donating eggs during the trial and for 4 weeks after the EOT visit. Effective contraceptive methods include combined (estrogen and progestogen containing) hormonal contraception associated with inhibition of ovulation (oral, intravaginal, transdermal); progestogen-only hormonal contraception associated with inhibition of ovulation (oral, injectable, implantable); intrauterine device; intrauterine hormone-releasing system; bilateral tubal occlusion; vasectomized partner. **In Germany**, oral methods of hormonal contraception are to be combined with another accepted method of contraception.

To be considered sterilized or infertile, females must have undergone surgical sterilization (bilateral tubectomy, hysterectomy, or bilateral ovariectomy) or be post-menopausal (defined as at least 12 months amenorrhea without an alternative medical cause, may be confirmed with follicle-stimulating hormone test in case of doubt). Women who do not engage in heterosexual intercourse will be allowed to join the trial without contraception following a thorough discussion with the Investigator to determine if this is feasible for the subject. The following methods are not considered acceptable methods of contraception: calendar, ovulation, symptothermal, post-ovulation methods, withdrawal (coitus interruptus), spermicides only, and lactational amenorrhea method

9. Male subjects with a female partner of childbearing potential must commit to practice methods of contraception and abstain from sperm donation during the trial and for 2 weeks after the EOT visit. Nevertheless, if their partners are women of childbearing potential, they must agree to practice contraception and use a highly effective method of contraception during the trial and for 4 weeks after the EOT visit. Such methods include combined (estrogen and progestogen containing) hormonal contraception associated with inhibition of ovulation (oral, intravaginal, transdermal); progestogen-only hormonal contraception associated with inhibition of ovulation (oral, injectable, implantable); intrauterine device; intrauterine hormone-releasing system; bilateral tubal occlusion

3.2.2 Exclusion Criteria

1. Treatment with any systemic GVHD therapy other than SS and RUX including methotrexate and mycophenolate mofetil at the time of randomization/Day 0. Graft versus host disease prophylaxis (ciclosporin A, tacrolimus, sirolimus, everolimus, or anti-thymocyte globulin) is allowed
2. Concomitant treatment with Janus kinase inhibitor therapy other than RUX at the time of randomization
3. Failed alloSCT due to relapse of underlying malignant disease
4. Presence of SR GI-aGVHD occurring after donor lymphocyte infusion for pre-emptive treatment of malignancy recurrence
5. Ongoing participation in an interventional trial or administration of any investigational drug in less than its five half-lives prior to randomization/Day 0. Participation in observational or interventional trials involving supportive care such as probiotics or antiemetics, graft manipulation or transplant procedures, new combinations or new dosing of approved therapies for conditioning, prophylaxis⁴, pre- or post-alloSCT and treatment of the underlying malignant disease are allowed after consultation with the Sponsor
6. Known or suspected hypersensitivity to GLP-1 or GLP-2 analogs or apaglutide excipients
7. Any use of enteral glutamine or growth factors such as native GLP-2, GLP-1, GLP-2 and GLP-1 analogs, or known ADA within 6 months prior to randomization/Day 0
8. Inability to understand or unwillingness to adhere to the trial visit schedules and other protocol requirements including those subjects not willing to comply owing to drug or alcohol abuse or any condition that would, in the Investigator's judgment, interfere with full participation in the trial, including administration of trial medication and attending required trial visits, pose a significant risk to the subject, or interfere with interpretation of trial data
9. Less than 2 weeks anticipated survival at screening
10. Evidence of chronic renal disease as demonstrated by inadequate renal function, which is defined as estimated glomerular filtration rate (eGFR) <20 mL/min/1.73 m² (using the Chronic Kidney Disease Epidemiology [CKD-EPI] formula) and is confirmed within 48 hours before randomization/Day 0
11. Presence of decompensated liver cirrhosis Child Pugh Classes B and C
12. Clinically significant or uncontrolled cardiac disease including acute myocardial infarction within 6 months prior to randomization/Day 0, uncontrolled hypertension, congestive heart failure New York Heart Association Class III or IV
13. Requirement for vasopressor or inotropic support within 30 days prior to randomization/Day 0
14. Presence of uncontrolled cholestatic disorders or unresolved sinusoidal obstructive syndrome/veno-occlusive disease of the liver (defined as

⁴ Except methotrexate and mycophenolate mofetil

persistent bilirubin abnormalities not attributable to aGVHD and ongoing organ dysfunction)

15. Presence of relapsed primary malignancy or treatment for relapse after alloSCT
16. Requirement for unplanned immune suppression withdrawal as treatment of early malignancy relapse or low donor chimerism. Unclear remission states will be discussed with the Sponsor
17. Presence of newly diagnosed malignancies at screening or prior to randomization/Day 0
18. History of chronic gall bladder or bile duct inflammation or biliary obstruction unless a cholecystectomy was performed before screening
19. Presence or history of GI tumors (including the hepatobiliary system and pancreas) within the last five years before randomization; presence of colonic polyps that are not removed
20. Subjects that present or have a history of familial adenomatous polyposis
21. Presence of an active clinically uncontrolled infection or evidence of active tuberculosis (clinical diagnosis per local practice). Cytomegalovirus reactivation is permitted as long as no evidence of pulmonary disease is present.
22. Central venous catheter sepsis requiring systemic antibiotics within the previous 7 days prior to randomization/Day 0
23. Known cGVHD
24. Known active GI inflammation not related to GI-aGVHD (e.g., active inflammatory bowel disease such as Crohn's and ulcerative colitis)
25. History of progressive multifocal leuko-encephalopathy
26. Known pregnant or nursing (lactating) women
27. Known major abdominal surgery in the last 6 months prior to randomization/Day 0 (surgical feeding tube placement or other minimally invasive surgery is allowed)
28. History of clinically significant intestinal adhesions increasing the risk of GI obstruction or GI contrast examination findings suggesting subacute intestinal obstruction or stricture within 6 months prior to randomization/Day 0
29. Liver enzymes meeting any of the following criteria within 48 hours prior to trial medication start:
 - a. Alanine aminotransferase (ALT) or aspartate aminotransferase (AST) $>8 \times$ upper limit of normal (ULN)
 - b. Alanine aminotransferase or AST $>5 \times$ ULN AND international normalized ratio >3

3.3 Lifestyle Considerations

Subjects will observe the contraception requirements laid out in inclusion criteria numbers 8 (female subjects) and 9 (male subjects).

Subjects should not use any drugs of abuse from screening until the EOT visit unless they have been prescribed (e.g., benzodiazepines).

4 TRIAL INTERVENTION/MEDICATION

4.1 Description of Investigational Medicinal Products

The IMP tested in this trial is apaglutide, a GLP-2 analog composed of 33 amino acids, containing natural and unnatural amino acids from non-animal origin. Apaglutide is manufactured by solid-phase peptide synthesis using 9-fluorenylmethyloxycarbonyl as an amine-protecting group. The formulation of apaglutide- is an aseptically manufactured freeze-dried powder for reconstitution with commercially available sterile water for injection. The IMP also contains the following excipients: glycine, L-histidine, mannitol, and sodium hydroxide. The pH of the reconstituted solution is approximately 8.3.

Apaglutide will be supplied in vials with 10 mg freeze-dried powder for reconstitution in sterile water prior to SC injection. Further details are provided in the Investigator's Brochure.

4.1.1 Packaging, Labeling, and Supply (Re-supply)

Packaging and labeling of the IMP is performed by the Clinical Trial Supplies vendor in accordance with Good Manufacturing Practice and applicable regulatory requirements.

The freeze-dried apaglutide powder is filled in 2-mL vials and sealed with rubber stoppers and aluminum caps. The subject boxes and individual vials will be labeled according to Annex 13, EudraLex Volume 4 [EudraLex Vol. 4, 2010] and national regulatory requirements.

All dosing will occur at the trial sites. Details are included in the Pharmacy Manual.

4.1.2 Storage Conditions

The Investigator must ensure that the IMP is stored between 2–8°C in a secure location with controlled access when at the site. At the site, the temperature will be monitored as described in the Pharmacy Manual and recorded in a temperature log as per the policies and guidelines of the site and prior to IMP dispensation. Any IMP experiencing temperature deviations outside the allowed range must be placed in quarantine (between 2–8°C) reported and evaluated prior to releasing it back into stock for use in the trial. Details are provided to the site in the Pharmacy Manual.

4.2 Administration of Experimental and Control Interventions

4.2.1 Experimental Intervention

4.2.1.1 Administration of Apraglutide

The dose to be administered to the subject at each time point depends on the treatment arm to which the subject is randomized and the subject's weight at baseline, as presented in Table 4. Non-randomized subjects with LBWs will only receive 2.5 mg of apraglutide.

Table 4: Dose of Investigational Medicinal Product Based on Treatment Arm and Weight

Treatment Arm	Weight Band (based on Baseline Weight)			
	40.0–<50.0 kg ¹	50.0–<60.0 kg	60.0–80.0 kg	>80.0 kg
Low dose (mg)	2.5	2.5	4	5
High dose (mg)		5	7.5	10

1. A non-randomized cohort of up to four subjects

The SC injection will be administered in the abdominal area or in the thigh. The injection site must be rotated such that an injection is administered at least 5 cm away from where the last injection was administered.

The IMP must be administered weekly as per scheduled (Table 1 and Table 2). Detailed instructions will be provided in the Pharmacy Manual for the site.

The Investigator is ultimately responsible for the appropriate preparation and administration of the IMP by assigning the appropriate site personnel and ensuring they are well-trained. The dose assigned through IRT will need to remain blinded to the subjects. Investigational medicinal product will not be administered to any person not enrolled in this trial.

4.2.1.2 Apraglutide Dose Adjustments, Interruptions and Stopping Rules

For subjects who do not tolerate the protocol dosing schedule, dose adjustments, or interruptions are mandated to allow the subjects to continue the trial medication and maintain apraglutide dosing for optimal treatment of aGVHD. The objective of these dose adjustment rules is to optimize response for each individual subject while avoiding clinically relevant toxicities attributed to apraglutide.

Dose reductions should be undertaken as outlined in Table 5.

Table 5: Dose Reduction Steps for Apraglutide

Original dose (mg)	2.5	4	5	7.5	10
New dose (mg)	0	2.5	4	5	7.5

Deviations to the recommended dose reductions, temporary interruptions, or permanent interruptions will need to be documented.

Subjects who are receiving multiple oncological treatments, or are dependent on parenteral support, develop abnormal liver function tests. In both cases bilirubin, ALT,

and/or AST may be elevated at baseline; therefore, the stopping rules for these subjects will use the increase from baseline instead of values from the ULN.

Table 6 depicts the dose adjustments for apaglutide dose in case of deviations of clinical safety parameters starting from Week 1.

Table 6: Apaglutide Dose Adjustments—Holding and Stopping Rules

Total bilirubin elevated (adapted from MAGIC)	
Use x ULN if normal at baseline (BSL) or x BSL if elevated at BSL	
>1.5–3.0 x ULN or BSL	Recommendation: Maintain dose level
>3.0–5.0 x ULN or BSL	
Mandatory: reduce by 1 dose level
 
Monitor LFTs weekly, or more frequently if clinically indicated, until resolved to $\leq 3.0 \times$ ULN/BSL:
 
 • If resolved in ≤ 14 days, then return to initial dose level • If resolved in >14 days, then maintain the dose level minus 1
>5.0–10.0 x ULN or BSL	
Mandatory: Hold dosing
 
Monitor LFTs weekly, or more frequently if clinically indicated, until resolved to $\leq 3.0 \times$ ULN/BSL:
 
 • If resolved in ≤ 14 days, then resume at initial dose level • If resolved in >14 days, then resume at dose level minus 1
>10.0 x ULN or BSL	
Mandatory: Hold dosing
 
Monitor LFTs weekly, or more frequently if clinically indicated, until resolved to $\leq 3.0 \times$ ULN/BSL:
 
 • If resolved in ≤ 14 days, then resume at dose level minus 1 • If resolved in >14 days, then STOP dosing 
The subject should be further monitored weekly (including LFTs), or more frequently if clinically indicated, until total bilirubin has resolved to baseline or stabilization over 4 weeks

AST or ALT elevated (normal BSL)	
>5.0–<8.0 x ULN for more than 2 weeks	
Mandatory: Hold dosing
 
Repeat LFTs as soon as possible, preferably within 48–72 hours from awareness of the abnormal results; monitor LFTs weekly, or more frequently if clinically indicated, until resolved to $\leq 5.0 \times$ ULN.
 
Then:
 
 • If resolved in ≤ 14 days (which start after 2 weeks of elevation), then resume at initial dose level • If resolved in >14 days (which start after 2 weeks of elevation), wait for resolution to ULN then resume at dose level minus 1

$\geq 8.0 - \leq 20.0 \times \text{ULN}$	
Mandatory: Hold dosing
 
Repeat LFTs as soon as possible, preferably within 48–72 hours from awareness of the abnormal results; monitor LFTs weekly, or more frequently if clinically indicated, until resolved to $\leq \text{ULN}$
 
Then resume at dose level minus 1

$>20.0 \times \text{ULN}$	Mandatory: STOP dosing
AST or ALT elevated (elevated at BSL)	
$>3.0 - <5.0 \times \text{BSL}$	
Mandatory: Hold dosing
 
Repeat LFTs as soon as possible, preferably within 48–72 hours from awareness of the abnormal results; monitor LFTs weekly, or more frequently if clinically indicated, until resolved to $\leq \text{BSL}$.
 
Then:
 
 • If resolved in ≤ 14 days, then resume same dose level • If resolved in >14 days, wait for resolution to BSL then resume at dose level minus 1
$\geq 5.0 - \leq 20.0 \times \text{BSL}$	
Mandatory: Hold dosing
 
Repeat LFTs as soon as possible, preferably within 48–72 hours from awareness of the abnormal results; monitor LFTs weekly, or more frequently if clinically indicated, until resolved to $\leq \text{BSL}$.
 
Then resume at dose level minus 1.

$>20.0 \times \text{BSL}$	Mandatory: STOP dosing
Combined AST/ALT and bilirubin elevation	
Use $\times \text{ULN}$ if normal at BSL or $\times \text{BSL}$ if elevated at BSL	
ALT/AST $>3.0 \times \text{ULN/BSL}$ and total bilirubin $>2.0 \times \text{ULN/BSL}$	
Mandatory: Hold dosing
 
Assess causality of the investigational compound:
 
 • If relationship to apaglutide is suspected (definitely, probably, possibly related) Stop dosing • If another cause is identified manage with institutional guidance and restart treatment
Asymptomatic amylase and/or lipase elevation	
$>1.0 - 1.5 \times \text{ULN}$	Recommendation: Maintain dose level
$>1.5 - 2.0 \times \text{ULN}$	Recommendation: Maintain dose level
$>2.0 - 5.0 \times \text{ULN}$	
Recommendation: Hold dosing until resolved to Grade ≤ 2, then:
 
 • If resolved in ≤ 7 days, then resume at same dose level • If resolved in >7 days, then resume at dose level minus 1
$>5.0 \times \text{ULN}$	Recommendation: Stop dosing
Pancreatitis	

Grade 2	Recommendation: Maintain dose level
Grade ≥ 3	Mandatory: Stop dosing
New onset of abdominal pain or worsening from BSL	
Grade ≥ 3	Mandatory: Stop dosing

ALT=alanine aminotransferase; AST=aspartate aminotransferase; BSL=baseline; LFT=liver function test; MAGIC=Mount Sinai Acute Graft Versus Host Disease International Consortium; ULN=upper limit of normal

Additional visits for unscheduled laboratory samplings or for safety reasons can be arranged as per the Investigator's judgment. In case of abnormal laboratory results of Common Terminology Criteria for Adverse Events (CTCAE) Grade 3 or higher assessed at a subject's local doctor, a re-assessment should be scheduled at the site.

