2.2.6 Early Treatment Discontinuation

A subject who discontinues treatment early is NOT considered to be withdrawn from the trial, but rather the subject will be followed up until the planned Week 104/EOT visit, provided that the subject's consent has not been withdrawn.

An early treatment discontinuation visit should be scheduled approximately 4 weeks (+1 week) from the last IMP dose. The subject will then transition to follow-up visits at Weeks 26, 52, and 104/EOT. The same visit should be completed also in case of early treatment discontinuation during the optional treatment period.

The decision for early treatment discontinuation can be made by the subject, the Investigator, or Sponsor personnel. A subject has the right to prematurely discontinue

trial medication at any time, without any justification, by withdrawal from trial medication only or by withdrawal from any further participation in the trial (i.e., early trial discontinuation [see Section 2.2.7]).

Although a subject is not obliged to give his/her reason for prematurely withdrawing from the treatment or the trial, it is recommended that the Investigator makes a reasonable effort to ascertain the reason(s), while fully respecting the subject's rights.

The Investigator must discontinue trial medication for a given subject if, on balance, he/she believes that continued administration would be contrary to the best interests of the subject.

A subject who discontinues treatment early and withdraws consent to participate in any further trial assessments is considered as withdrawn from the trial and no further assessment will be collected after informed consent withdrawal.

Apaglutide should be permanently stopped under the following conditions:

- New malignancy is identified during the trial (subjects must be treated and followed up as per local guidelines and practices for those malignancies)
- In case of an elevation of laboratory parameters as reported in Table 6
- The subject is pregnant
- In case of unacceptable toxicities associated (definitely, probably, possibly related) with apaglutide

For further considerations on IMP dose reduction and temporary discontinuation, see Section 6.6.2.

The Investigator must discontinue trial medication for a given subject if, on balance, he/she believes that continued administration would be contrary to the best interests of the subject.

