6.6 Trial Specific Safety Considerations

6.6.1 Overdose

Details of overdose of apaglutide or any concomitant therapy must be recorded in the eCRF and on the dedicated paper form to be included into the Safety Database. Any overdose that is considered by the Investigator to be clinically significant must be reported as an SAE in the eCRF.

6.6.2 Considerations on Investigational Medicinal Product Dose Reduction and Temporary Discontinuation

If the Investigator reduces the dose of the IMP because of documented safety reasons, the safety reasons should be documented as an AE.

Reduction of IMP means reducing the dose by one step (see Table 5) or pausing in case of general tolerability issues. The IMP dose can only be reduced by one step during the trial.

For specific dose adjustments of apaglutide in cases of abnormal liver function tests, bilirubin, or other clinical chemical parameters, refer to Section 4.2. **The Investigator should attempt to return to the per protocol dose as soon as the medical condition of the subject allows and a new weekly schedule of IMP administration may be established.** If the subject does not continue to tolerate the per protocol dose the Investigator may choose to resume IMP administration at the weekly lower dose.

Changes and discontinuations must be reported to the CRA in charge of the site and discussed with the Medical Monitor. If the subject's medical condition allows, this discussion may occur before any dose change/discontinuation but must occur after if not possible (e.g., an AE necessitating an immediate stop to dosing with apaglutide). The final decision to reduce or discontinue IMP rests with the Investigator.

Dose changes and the rationale will be documented in the medical records, and in the eCRF. Missed doses (scheduled doses that have not been taken) will not be made up for, i.e., the treatment period will not be prolonged due to temporary discontinuation. Missed doses should be reported as a protocol deviation.

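### Table 6's combined ALT/AST-plus-bilirubin row allows restart with no upper bound and conflicts with the table's own STOP rows in two narrow overlaps

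*Protocol*

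**What the plan says.** Table 6 (Protocol Section 4.2.1.2) sets the apraglutide holding and stopping rules from Week 1. Multiples refer to ULN if the parameter was normal at baseline and to the baseline value (BSL) if it was elevated. Three liver entries matter here.

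- **ALT/AST above 20.0 × ULN, or above 20.0 × BSL:** "Mandatory: STOP dosing". No causality condition is attached.
- **Total bilirubin above 10.0 ×:** hold and monitor until 3.0 × or below. If that takes 14 days or less, resume one dose level down. If it takes longer, "then STOP dosing". Again, cause plays no part.
- **ALT/AST above 3.0 × together with bilirubin above 2.0 ×:** hold and assess causality. If a relationship to apraglutide "is suspected (definitely, probably, possibly related) Stop dosing". Otherwise: "If another cause is identified manage with institutional guidance and restart treatment".

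Section 2.2.6 says apraglutide "should be permanently stopped under the following conditions" and lists among them "In case of an elevation of laboratory parameters as reported in Table 6". Section 6.6.2 sends liver cases back to Section 4.2 and adds two procedural points: "Changes and discontinuations must be reported to the CRA in charge of the site and discussed with the Medical Monitor", and "The final decision to reduce or discontinue IMP rests with the Investigator".

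**The concern.** The combined row is entered on lower bounds only, so it stays in force however high the two values go. Once a non-drug cause is found it points to restart, including at values where a single-parameter row has ordered a stop regardless of cause. Neither Section 4.2.1.2 nor the notes to Table 6 say which row governs when two apply.

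Two sites could then treat the same laboratory picture differently, both following the table. If a site takes the combined row as the more specific one, a worse liver picture gets the more lenient instruction: ALT/AST above 20 × alone is a permanent stop, while the same ALT/AST with raised bilirubin may be restarted. What is at stake is re-exposure of an individual subject after severe liver abnormality.

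**Working it through.** The plan states no figure to reproduce, so the check is logical. Let A be the ALT/AST multiple, B the total bilirubin multiple, and D the days for bilirubin to reach 3.0 × or below, each on the ULN or BSL scale that Table 6 prescribes. Assume another cause has been identified.

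**Conditions from Table 6**

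- Combined row, restart branch: A > 3 and B > 2.
- ALT/AST STOP: A > 20.
- Bilirubin STOP: B > 10 and D > 14.

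**Where restart and STOP both apply**

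Intersect the first condition with either of the other two. Because 20 > 3 and 10 > 2, this reduces to:

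1. A > 20 and B > 2; or
2. A > 3, B > 10 and D > 14.

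Both can hold at once. No other values that meet the combined row meet a liver STOP row. The result is the same for normal and elevated baseline. The Grade 3 or higher pancreatitis and abdominal-pain STOP rows rest on separate clinical events and are not counted.

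**Paired cases, normal baseline, another cause identified**

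| A | B | D | Single-parameter rows | Combined row | Instruction |
|---|---|---|---|---|---|
| 25 | 1.5 | – | ALT/AST: STOP | not met (B not above 2) | STOP only |
| 25 | 2.5 | – | ALT/AST: STOP; bilirubin: maintain | hold, then restart | STOP and restart |
| 2 | 12 | 21 | bilirubin: STOP (21 > 14) | not met (A not above 3) | STOP only |
| 4 | 12 | 21 | bilirubin: STOP (21 > 14) | hold, then restart | STOP and restart |
| 4 | 12 | 10 | bilirubin: resume at minus 1 | hold, then restart | no STOP row met |

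Within each overlap, making the second parameter worse adds a restart instruction that the milder case does not have.

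**Reach of the first overlap**

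For elevated baseline the ALT/AST threshold is 20 × BSL. A baseline of 3 × ULN needs more than 20 × 3 = 60 × ULN. At the eligibility ceiling of 8 × ULN (exclusion criterion 29) it needs more than 20 × 8 = 160 × ULN. The first overlap is therefore mainly a normal-baseline case.

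**Does other text settle it?**

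- Section 2.2.6 points to Table 6 as a whole, which also holds maintain, reduce, hold and restart entries. It ranks none of them.
- Section 4.2.1.2 gives its aim as keeping subjects on treatment while avoiding toxicity attributed to apraglutide. Section 6.6.2 asks the investigator to try to return to the protocol dose once the subject's condition allows. Both make the restart reading available to a site that has found another cause.

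**The case against.** The strongest answer is that the rows are separate triggers. On that view the restart bullet only says when the combined row's own hold ends, and ending one hold does not cancel a mandatory stop under another row. Section 2.2.6 supports this: its permanent-stop clause cannot sensibly cover rows that provide for resumption, so it most naturally refers to the STOP rows. This stands as the sensible reading. It remains an inference, because no sentence states it and other text pulls towards restart.

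The combined row is also stricter in one respect: even a possible relationship to apraglutide stops dosing, and restart needs another cause to be identified. That is correct. But the conflict arises precisely in subjects who have passed that test.

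Safeguards exist. Changes are discussed with the Medical Monitor, the investigator decides, and Section 2.2.6 obliges the investigator to stop when dosing is against the subject's interests. Under Section 6.6.3, stops or holds for ALT/AST and/or bilirubin elevation count towards the toxicity rule. One event triggers iSRC review while one to six subjects have been randomized, and dosing is suspended during the review. A parenthesis about confirmed Hy's law cases may narrow which events count. These measures reduce the risk, but none says which row applies to the individual subject.

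Finally, timing. The SAP (Section 1) sets the primary-analysis cut-off at 01 Dec 2023, with all enrolled subjects at Day 91 or withdrawn. The last possible dose is at Week 25, or Day 175. That is at most 175 − 91 = 84 days later, in late February 2024. This limits the practical value for subjects in this trial but does not change what the table says.

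**Conclusion.** The point holds as a minor subject-safety inconsistency. As written, Table 6 gives both STOP and restart in exactly two liver overlaps when a non-drug cause has been identified, and no text states precedence.

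Three stronger inferences are not supported:

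- **That the protocol directs sites to rechallenge after severe liver injury.** Both rows withdraw drug at first, restart needs an identified other cause, and Section 2.2.6 leans towards STOP.
- **That the conflict is common.** It needs extreme values plus an identified other cause. The documents give no event frequency, so no probability can be stated, and counting combinations of bands in the table would say nothing about likelihood.
- **That efficacy results are compromised.** The efficacy analyses stay as planned: the Day 56 estimand in SAP Section 4.3.9.2 uses observed values after discontinuation and after a pause alike.

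The conclusion rests on reading each row at its stated thresholds, with each parameter on its own ULN or BSL scale.

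**What to change.** Amend the restart bullet of the combined row so that it applies only if another cause is identified *and no single-parameter STOP row is met*. The rest of the bullet stays as it is. This removes both overlaps and leaves every combination that meets no STOP row unchanged.

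A general rule that the most restrictive row always wins would go further than needed. With ALT/AST at 4 × and bilirubin at 12 × resolved on day 10, for example, it would impose dose level minus 1 where the combined row names no dose. Whether that row should state a recovery level and restart dose is a separate clinical decision for the sponsor.

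Cost: a few subjects with a clear non-drug cause stop permanently, as the STOP rows already require. Because the change alters a mandatory dosing rule, it would normally need IEC/IRB/CA approval under Section 9.6; a site letter alone would not do. Sample size, visits and analyses are unaffected.
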